9.2 Background Characteristics

9.2.1 Subject Disposition

A disposition table will be provided for the Run-in Period with the following categories:

- All Subjects Set
- Safety Set for the Run-in Period

The number and percentage (based on Safety Set for the Run-in Period) of subjects in each of the following disposition categories will be summarized:

- Completed run-in period treatment
- Prematurely discontinued Run-in period treatment and the reason for treatment discontinuation
- Prematurely discontinued study in Run-in Period and the reason for study discontinuation

A separate disposition table will be provided for the Treatment Period with the following categories:

- Full Analysis Set
- Safety Set for the Treatment Period
- Randomized
- Randomized but not dosed in the Treatment Period
- Randomized or dosed in the Treatment Period

The number and percentage (based on Safety Set for the Treatment Period) of subjects in each of the following disposition categories will be summarized by treatment group and overall:

- Completed study drug treatment
- Prematurely discontinued treatment and the reason for discontinuation (i.e., discontinued all study drugs)
- Completed study
- Prematurely discontinued the study and the reason for discontinuation
- Rollover to the open-label study

A listing will be provided for subjects who discontinued treatment (including both the Run-in Period and Treatment Period) or who discontinued study with reasons for discontinuation.

9.2.2 Demographics and Baseline Characteristics

Demographics and baseline characteristics will be summarized based on the FAS, and presented by treatment group and overall, as applicable.

Demographic data will include the following:

- Age at baseline (in years)
- Sex (female and male)

- Ethnicity (Hispanic or Latino, not Hispanic or Latino, and not collected per local regulations)
- Race (White, Black or African American, Asian, American Indian or Alaska Native, Native Hawaiian or Other Pacific Islander, and not collected per local regulations)
- Geographic region (North America, Europe [including Australia])

Baseline characteristics will include the following:

- Weight (kg)
- Height (cm)
- BMI (kg/m²)
- Age group at the Screening Visit (≥ 12 to < 18 , ≥ 18)

Stratification categories will include the following:

- Comparator group (TEZ/IVA, IVA)
- ppFEV₁ at Day -14 (< 70 , ≥ 70)
- Sweat Chloride at Day -14 (< 30 mmol/L, ≥ 30 mmol/L)

Disease characteristics will include the following:

- ppFEV₁ category at baseline (< 40 , ≥ 40 to < 70 , ≥ 70 to ≤ 90 , and > 90)
- ppFEV₁ at baseline (continuous)
- Sweat chloride at baseline (continuous)
- CFQ-R respiratory domain score at baseline (continuous)
- Prior use of dornase alfa before first dose of study drug in the Treatment Period (Yes, No)
- Prior use of azithromycin before first dose of study drug in the Treatment Period (Yes, No)
- Prior use of inhaled antibiotic before first dose of study drug in the Treatment Period (Yes, No)
- Prior use of bronchodilator before first dose of study drug in the Treatment Period (Yes, No)
- Prior use of inhaled bronchodilator before first dose of study drug in the Treatment Period (Yes, No)
- Prior use of inhaled hypertonic saline before first dose of study drug in the Treatment Period (Yes, No)
- Infection with *Pseudomonas aeruginosa* within 2 years prior to screening (Positive, Negative)

In addition, data listings will also be provided for:

- Informed consent;
- Inclusion/Exclusion criteria violation for subjects with any such violations.

9.2.3 Medical History

Medical history will be coded by using the Medical Dictionary for Regulatory Activities (MedDRA). Medical history will be summarized descriptively by System Organ Class and Preferred Term based on the FAS. The corresponding data listing will also be provided.

In addition, the number of subjects reported to have had positive cultures for respiratory pathogens within the 2 years prior to screening (i.e., answered yes on the respiratory microbiology form) will be summarized for the FAS. The corresponding data listing will be provided.

9.2.4 Prior and Concomitant Medications

Medications will be coded using the World Health Organization Drug Dictionary (WHO-DD) and categorized as follows:

Prior medication: any medication that was administered during the 56 days before the first dose date of study drug in the Treatment Period but not in the Run-in Period. For subjects who discontinue during Run-in Period and whose first dose of study drug in the Treatment Period is not available, prior medication will be any medication that was administered during the 56 days prior to the last dose date in the Run-in Period but before the first dose date in the Run-in Period.

Concomitant medication during the Run-in Period: medication continued or newly received during the TE period for the Run-in Period.

Concomitant medication during the Treatment Period: medication continued or newly received during the TE period for the Treatment Period.

Post-treatment medication: medication continued or newly received after:

- the TE period for the Run-in Period if the subject did not receive study drug in the Treatment Period.
- the TE period for the Treatment Period for subjects who received study drug in the Treatment Period.

A given medication may be classified as any combination of the above categories, for example, prior and concomitant during the Run-in Period, concomitant during the Treatment Period and post-treatment, or concomitant for both periods and post-treatment.

If a medication has completely missing or partially missing start/stop date and if it cannot be determined whether it was taken before the first dose date of study drug, concomitantly, or after the TE period, it will be classified as prior, concomitant for both periods, and post-treatment. Details for imputing missing or partial start and/or stop dates of medication are described in [Appendix B](#).

Prior medications and concomitant medications will be summarized descriptively based on the FAS using frequency tables by: 1) treatment group and overall, preferred name (PN); and 2) treatment group and overall, anatomic class (ATC) level 1, ATC level 2, and PN.

Prior and concomitant medication during the Run-in Period will be summarized together in one summary table. Post-treatment medications will be listed in the all medication listing.

9.2.5 Study Drug Exposure

Study drug exposure will be summarized for the Treatment Period only based on the Safety Set for the Treatment Period, and will be presented by treatment group and overall.

Duration of study drug exposure (in days) will be calculated as: last dose date of study drug in the Treatment Period – first dose date of study drug in the Treatment Period + 1, regardless of study drug interruption, and will be summarized descriptively.

Study drug exposure (in weeks) will be summarized descriptively by the number of subjects (n), mean, SD, median, min, and max. It will also be summarized by interval: ≤ 2 weeks, $>2- \leq 4$ weeks, $>4- \leq 8$ and >8 weeks, using counts and percentages. Additionally, the total study drug exposure, defined as the sum total of the study drug exposure across all subjects (in patient-weeks), will be provided.

9.2.6 Study Drug Compliance

Study drug compliance will be summarized for the Treatment Period only based on the FAS, and will be presented by treatment group and overall.

Study drug compliance will be calculated as: $100 \times [1 - (\text{total number of days of study drug interruption during the Treatment Period}) / (\text{duration of study drug exposure in days during the Treatment Period})]$. A study drug interruption on a given day is defined as an interruption of any study drugs on that day. A study drug interruption that continues through the end of the study participation (i.e., subject does not resume study drug before the end of the study participation) will not be included in the compliance calculation.

Study drug compliance will be summarized descriptively by the number of subjects (n), mean, SD, median, min, and max. It will also be summarized in categories: $<80\%$ and $\geq 80\%$ using frequency tables.

In addition, percentage of tablets taken will be calculated using the following formula: $100 \times [(\text{total number of tablets dispensed for the Treatment Period}) - (\text{total number of tablets returned for the Treatment Period})] / (\text{total number of tablets planned to be taken per day} \times \text{duration of study drug exposure in days for the Treatment Period})$. Summary similar to those for the study drug compliance will be produced based on the FAS.

9.2.7 Important Protocol Deviations

An important protocol deviation (IPD) is a deviation that may significantly affect the completeness, accuracy, or reliability of the study data or that may significantly affect a subject's rights, safety, or well-being. IPD rules will be developed and finalized before database lock.

The protocol deviations that should be considered as potential IPDs include, but are not limited to:

- Subject was enrolled in the study despite the violation of inclusion/exclusion criteria
- Subject was less than 80% compliant with study drug for non-safety reasons
- Subject received prohibited concomitant medications
- Subject received the wrong treatment or incorrect doses

Occurrence of any of these events should be considered as potential IPDs, but a blinded team should categorize them as IPDs only if they have the potential to significantly affect the completeness, accuracy, or reliability of the study data or that may significantly affect a subject's rights, safety, or well-being.

IPDs (from the site deviation log) will be summarized descriptively based on the FAS and presented by treatment group and overall. Additionally, IPDs will be provided in an individual subject data listing.

9.3 Efficacy Analysis

Unless otherwise defined, all efficacy analyses described in this section will be based on the FAS.

9.3.1 Analysis of Primary Efficacy Variable

9.3.1.1 Definition of Variable

The primary efficacy variable is absolute change in ppFEV₁ from baseline through Week 8 for the ELX/TEZ/IVA group. Percent predicted FEV₁ is the ratio of FEV₁ (L) to the predicted FEV₁ (L), expressed as a percentage. The predicted FEV₁ will be calculated using the Global Lung Function Initiative¹ (GLI); details are in [Appendix C](#).

9.3.1.2 Primary Analysis

The primary analysis will be performed using a mixed-effects model for repeated measures (MMRM) with the absolute change from baseline at Day 15, Week 4 and Week 8 as the dependent variable. The model will include treatment group, visit, and treatment-by-visit interaction as fixed effects, with continuous baseline ppFEV₁, continuous baseline SwCl, and comparator group (IVA comparator versus TEZ/IVA comparator) as covariates. The Day 15 Visit will not be included in the estimation of the average treatment effect through Week 8. The model will be estimated using restricted maximum likelihood. Denominator degrees of freedom for the *F*-test for fixed effects will be estimated using the Kenward-Roger approximation². An unstructured covariance structure will be used to model the within-subject errors. If the model estimation does not converge, a compound symmetry covariance structure will be used instead. Conditional on the observed data and covariates, missing data will be assumed to be missing at random; consequently, no imputation of missing data will be performed.

The primary results obtained from the model will be the estimated within-group treatment difference through Week 8 (average of Week 4 and Week 8) for the ELX/TEZ/IVA group. The adjusted means with 2-sided 95% confidence intervals and 2-sided *P* values will be provided. Furthermore, the within-group treatment difference at each post-baseline visit will also be provided, obtained from the model.

The adjusted mean (with SE) obtained from the MMRM analysis at each post-baseline visit up to Week 8 will be plotted by treatment group.

The primary analysis will be conducted with the clinic spirometry data only. An additional analysis may also be performed to include pooled spirometry data obtained in clinic and by Air Next Spirometer, if the Air Next Spirometry data are assessed to be reasonably consistent with clinic spirometry data.

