9.1.2 Run-in Period

The Run-in Period has a 4-week duration and is designed to establish a reliable on-treatment (IVA for the IVA comparator group and TEZ/IVA for the TEZ/IVA comparator group) baseline for the Treatment Period. The first dose of open-label IVA or TEZ/IVA (as applicable) will be administered at the Day -28 Visit. The last dose of open-label IVA will be administered in the evening on Day -1 (1 day before the Day 1 Visit).

A subject's screening *CFTR* genotype **must** confirm eligibility before the subject enters the Run-in Period (Section 11.6.2).

On Day -14, spirometry and SwCl will be assessed. The Day -14 spirometry and SwCl assessments will be used for stratification of randomization (Section 9.2).

Subjects who prematurely discontinue study drug treatment during the Run-in Period will not be randomized or participate in the Treatment Period (Section 9.1.5.1) and are not permitted to rescreen.

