7.2 Sample Size and Power

The primary efficacy endpoint is the absolute change in ppFEV₁ from baseline through Week 8 for the ELX/TEZ/IVA group. The primary null hypothesis to be tested is that the mean absolute change in ppFEV₁ from baseline through Week 8 is 0 for the ELX/TEZ/IVA treatment group. The null hypothesis will be tested at a 2-sided significance level of 0.05.

For the primary hypothesis, assuming a within-group standard deviation (SD) of 7.0 percentage points and a 10% dropout rate at Week 8, a sample size of 125 subjects in the ELX/TEZ/IVA arm will have >99% power to detect the within group difference of 3.0 percentage points (1 sample t test at a 2-sided significance level of 0.05).

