7.3 Randomization

Randomization will be stratified based on comparator group (IVA comparator versus TEZ/IVA comparator), ppFEV₁ as determined during the Run-in Period (Day -14 assessment; <70 versus ≥70), and SwCl as determined during the Run-in Period (Day -14 assessment; <30 mmol/L versus ≥30 mmol/L).

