9 STATISTICAL ANALYSIS

9.1 General Considerations

The Schedule of Assessments is provided in Section 3 of CSP. The precision standards for reporting safety and efficacy variables are provided in an internal Biometrics document that specifies the programming rules including the precision for derived variables.

Continuous variables will be summarized using the following descriptive summary statistics: the number of subjects (n), mean, standard deviation (SD), median, minimum value (min), and maximum value (max).

Categorical variables will be summarized using counts and percentages. Percentages will be presented to 1 decimal place.

Baseline value, unless otherwise specified, is defined as the most recent non-missing measurement (scheduled or unscheduled) collected before the first dose of study drug in the Treatment Period (i.e., the Day 1 Visit). For ECGs, baseline will be defined as the most recent pretreatment measurement before the first dose of study drug in the Treatment Period (i.e., the Day 1 Visit).

Absolute change from baseline will be calculated as post-baseline value - baseline value.

Relative change from baseline will be calculated as (post-baseline value - baseline value)/baseline value.

The **Treatment-emergent (TE) Period for the Run-in Period** will be from the first dose of study drug in the Run-in Period to (1) the first dose of study drug in the Treatment Period for subjects who complete the Run-in Period and continue to the Treatment Period, or (2) 28 days after the last dose date of study drug in the Run-in Period or to the completion of study participation date, whichever occurs first, for subjects who do not continue to the Treatment Period (e.g., subjects who do not meet the conditions to enter the Treatment Period).

The **TE Period for the Treatment Period** will include the time from the first dose date of study drug in the Treatment Period (TC, placebo + TEZ/IVA, or placebo + IVA) to 28 days after the last dose of the study drug or to the completion of study participation date, whichever occurs first.

Unscheduled visits: Unscheduled visit measurements will be included in analysis as follows:

- 1) In scheduled visit windows per specified visit windowing rules
- 2) In the derivation of baseline
- 3) In the derivation of maximum and minimum values during TE period, and maximum and minimum change from baseline values during TE period for safety analyses
- 4) In individual subject data listings as appropriate

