9.3.2.2 Analysis Method

Absolute change in SwCl from baseline through Week 8 for the ELX/TEZ/IVA group:

Analysis of this endpoint will be based on the same MMRM model as the analysis of the primary efficacy endpoint. Data obtained from the Day 15, Week 4, and Week 8 Visits will be included in the model. Absolute change in SwCl from baseline through Week 8 is defined as average of Day 15, Week 4, and Week 8.

Absolute change in ppFEV₁ from baseline through Week 8 for the ELX/TEZ/IVA group compared to the control group:

Analysis of this endpoint will be based on the same MMRM model as the analysis of the primary efficacy endpoint. Data obtained from the Day 15, Week 4, and Week 8 Visits will be included in the model. However, the Day 15 Visit will not be included in the estimation of the average treatment effect through Week 8.

Absolute change in SwCl from baseline through Week 8 for the ELX/TEZ/IVA group compared to the control group:

Analysis of this endpoint will be based on the same MMRM model as the analysis of the primary efficacy endpoint. Data obtained from the Day 15, Week 4, and Week 8 Visits will be included in the model. Absolute change in SwCl from baseline through Week 8 is defined as average of Day 15, Week 4, and Week 8.

The LS mean (SE) of the within-treatment group change from baseline at each post-baseline visit up to Week 8 along with the 95% CI will be estimated from the corresponding MMRM. The LS mean (SE) of the treatment difference between ELX/TEZ/IVA and control at each post-baseline visit will be provided along with the corresponding 95% CI and *P* value. The LS mean (SE) at each visit will also be plotted by treatment group. In addition, the post-baseline raw values and the absolute change from baseline at each post-baseline visit up to Week 8 will be summarized descriptively (n, mean, SD, median, minimum, and maximum).

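### The models for the between-arm key secondary endpoints leave out the Day -14 ppFEV₁ and sweat chloride values, and so probably forgo some precision

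*SAP*

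**What the plan says.** Protocol Table 3-2 schedules both tests at Day -14 and again at Day 1. The stated use of the first pair is this: "The Day -14 spirometry and SwCl assessments will be used for stratification of randomization" (Protocol 9.1.2). For that purpose they are dichotomised. SAP 7.3 gives, for lung function, "ppFEV₁ as determined during the Run-in Period (Day -14 assessment; <70 versus ≥70", and cuts SwCl at 30 mmol/L. SAP 9.2.2 tabulates them in the same categories.

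The analysis uses a different value. SAP 9.1 states: "Baseline value, unless otherwise specified, is defined as the most recent non-missing measurement (scheduled or unscheduled) collected before the first dose". With the schedule followed, that is Day 1. SAP 9.3.1.2 then fits the MMRM "with continuous baseline ppFEV₁, continuous baseline SwCl, and comparator group (IVA comparator versus TEZ/IVA comparator) as covariates". For each key secondary endpoint SAP 9.3.2.2 says: "Analysis of this endpoint will be based on the same MMRM model as the analysis of the primary efficacy endpoint". No Day -14 term appears in any model, continuous or dichotomised.

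Two further provisions matter. Protocol 9.2 allows for a Day -14 value that is invalid or unavailable, and then stratifies on the most recent valid value. Under the baseline rule, a Day -14 value becomes the baseline when no later pre-dose value exists.

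**The concern.** A single Day 1 reading carries all of that day's measurement noise. A second on-treatment reading taken before randomisation can remove part of that noise from the residual variance, and adjusting for it cannot bias a randomised comparison. The reading is already being collected.

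Key secondary endpoints 2 and 3 are where this counts. The primary endpoint and the first key secondary endpoint are within-arm changes from baseline. Only endpoints 2 and 3 use the randomised control, and the sample-size section states no power, effect or SD for them. At stake is the width of the two between-arm intervals and the power of those tests. The validity of the tests is not in question.

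**Working it through.** **1. The plan's own figure.** SAP 7.2 takes a two-sided 5% level, an SD of 7.0 points and 10% loss by Week 8. It concludes: "a sample size of 125 subjects in the ELX/TEZ/IVA arm will have >99% power to detect the within group difference of 3.0 percentage points". Evaluable n = 125 × 0.9 = 112.5, taken as 112. Noncentrality = 3.0 / (7.0/√112) = 4.54, and the one-sample *t*-test power is 99.4%. The stated figure is confirmed, but it covers only the within-arm test.

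**2. Method for the between-arm ppFEV₁ difference.** Let Y be the mean of Weeks 4 and 8. Given pre-treatment covariates, its residual variance is v − c′S⁻¹c, where v = Var(Y), S is the covariance matrix of the covariates and c is their covariance with Y. The SE of the arm difference is proportional to the square root of this. Data are taken as complete.

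From the plan: change SD 7.0 and 112 per arm. Assumed: between-subject SD 15 (variance 225), the within-subject covariance structure, and a between-arm difference of 3.0. In the plan 3.0 is a within-group figure.

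**3. Most favourable structure: independent visit noise w.**
- Calibration: w(1 + ½) = 49, so w = 32.67
- v = 225 + 32.67/2 = 241.33; each pre-treatment value has variance 257.67; each covariance is 225
- Day 1 only: 241.33 − 225²/257.67 = 44.86
- Day 1 and Day -14: 241.33 − 2 × 225²/(257.67 + 225) = 31.56
- SE ratio √(31.56/44.86) = 0.839, a 16% cut, equivalent to 44.86/31.56 = 1.42 times the patients
- Power Φ(3.0/[SD × √(2/112)] − 1.96): SD 6.70 gives 91.8%; SD 5.62 gives 97.9%

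**4. Less favourable structures, same formula.**

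| Within-subject variance | SE ratio | SE cut |
|---|---|---|
| All independent noise | 0.84 | 16% |
| Half independent, half decaying (half-life 14–28 days) | 0.89–0.90 | 10–11% |
| All decaying (half-life 14–28 days) | 0.94–0.98 | 2–6% |

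In the middle row, at 28 days, power goes from 91.6% to 95.9%.

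**5. What shrinks it further.**
- *Varying response.* Assume a response SD of 5 in the ELX arm, with that arm's change SD held at 7. Then w = (49 − 25)/1.5 = 16. The noise part of the residual is 233 − 225²/241 = 22.94 with Day 1 only, and 233 − 2 × 225²/(241 + 225) = 15.73 with both. Averaged over the arms, response variance adds 25/2 = 12.5, giving 35.44 and 28.23. The ratio is √(28.23/35.44) = 0.892, an 11% cut. With all noise decaying the cut is 2–4%. Power is already about 96% and rises to 97–99%.
- *Unsettled Day -14.* Five extra points of SD at Day -14 (assumed) leave a cut of 1–11%.
- *Purely first-order autoregressive values.* Given Day 1, Day -14 then adds nothing, and the cut is zero.

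**6. SwCl, mean of three visits.** With exchangeable correlation ρ and k pre-treatment values, the residual variance is proportional to (1 − ρ)[1/3 + ρ/(1 + (k − 1)ρ)].
- ρ = 0.6: 0.3733 falls to 0.2833; ratio 0.871, a 13% cut
- ρ = 0.9: 0.1233 falls to 0.0807; ratio 0.809, a 19% cut

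Under a purely autoregressive process it is again zero. SwCl power cannot be computed, because the documents give no SwCl SD or effect.

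**7. Missing Day -14 values.** Take a middle case in which complete data give a 14–15% cut in residual variance. If subjects without Day -14 drop out of the model, a simulation gives a net gain of 12% at 3% missing, 9% at 5%, 4% at 10% and about −1% at 15%. A rule for missing values is therefore essential.

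**The case against.** The planned model is a legitimate choice. It is unbiased and controls type I error. It contains comparator group, and it carries the other two stratification variables as continuous values measured about two weeks later. A reader might infer that two of the three randomisation factors are ignored. The documents do not support that: their Day -14 categories are absent, but the quantities themselves are largely adjusted for.

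The size depends on inputs that the plan does not give, and the 16% figure needs independent noise and no variation in response. Day -14 is also the midpoint of a four-week run-in meant to establish the on-treatment baseline, so it may not replicate Day 1. Both points stand, and they are why the result is a range.

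Reusing the stratification value for a missing Day -14 would be unsound. Neither test is scheduled at Day -28, so the substitute would normally be a screening value. That predates the run-in drug and, for spirometry, may be post-bronchodilator (Protocol 11.5.1). If randomisation is on Day 1, it could be the Day 1 value itself. This stands, and the fix avoids it.

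The protocol synopsis and Protocol 12.3.3.2 tie the within-arm and between-arm estimates to one model, and SAP 3.1 lists no departures from the protocol. This also stands: the change needs more than one added sentence. None of these points removes the likely gain.

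**Conclusion.** The concern holds as a missed efficiency in a valid analysis. Under the assumptions shown, the SE of the between-arm ppFEV₁ difference falls by about 2–16% (2–11% with an ELX response SD of 5 points, near zero at worst). For SwCl the cut is 13–19% under exchangeable visits, and less if correlation decays. The cost is one model degree of freedom per endpoint among about 225 subjects.

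Three stronger readings are tempting and not supported:
- *Every randomised subject has a second value, used only to stratify.* Protocol 9.2 foresees missing or invalid values, and the baseline rule can turn Day -14 into the baseline.
- *Precision is certainly wasted, to the extent of 42% more patients.* That is the best case of the range.
- *The between-arm tests are underpowered.* Under the assumed 3.0-point difference, power without Day -14 is about 91–92%, or about 96% with the response SD of 5.

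**What to change.** Before database lock, as SAP Section 4 allows:
- In SAP 9.3.2.2, add continuous Day -14 ppFEV₁ to the model for key secondary endpoint 2 and continuous Day -14 SwCl to the model for key secondary endpoint 3, beside the existing covariates.
- Leave the models for the primary endpoint and key secondary endpoint 1 unchanged.
- If Day -14 is missing, invalid or is itself the baseline, impute the covariate blind to treatment: from the Day 1 value where there is one, otherwise by the overall mean. No subject is then dropped and no screening value is substituted.
- Reword the same-model sentences for endpoints 2 and 3 in SAP 9.3.2.2, and its closing paragraph, which takes within-group means and differences from one model. Record the departure from the protocol's wording in SAP 3.1.

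The downside is small and should be stated in the SAP: the between-arm estimate will not exactly equal the difference of the reported within-arm means. No new data are needed.
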